**Table 3 Part 2 – 7-Day Repeat Dose Escalation (Days 1 and 7)**

Procedure	Study Days													Notes
	1 and 7													
	-1	Predose	0	0.25	0.5	1	1.5	2	4	6	8	12	16	Hours relative to study intervention
Inclusion and exclusion criteria	X													Recheck clinical status before randomization and/or 1 st dose of study treatment
Brief physical examination	X													
Urine Drug, Smoke Breathalyzer/Alcohol Breath Tests	X													Additional testing may be performed at other timepoints
β-hCG pregnancy test	X													Pregnancy test as appropriate
Admission to clinical unit	X													
Randomization		X												Randomization will occur before first dose on Day 1 only.
Administration of study intervention			X											
AE Review			X	←	Continuous review									
SAE Review				←	Continuous review									Serious AEs will be collected from the signing of informed consent.
Ad hoc COVID-19 testing based on clinical presentation and site procedures				←	Continuous review									
Concomitant medication review			X	←	Continuous review									

Procedure	Study Days													Notes
	1 and 7													
	-1	Predose	0	0.25	0.5	1	1.5	2	4	6	8	12	16	Hours relative to study intervention
Vital signs (BP, HR, tympanic temperature, respiration rate)	X	X*				X		X	X	X	X			Vital signs will be obtained within 1 hour of pre-dose and at 1, 2, 4, 6, 8, 12 and 24 hours after study administration on Days 1 and 7.  *Triplicate readings of blood pressure and pulse rate will be taken pre-dose and averaged on Days 1 and 7.  Single measurements will be obtained at all other timepoints.  Timings will be reviewed as cohorts progress and may be adjusted to ensure appropriate measurements relative to peak concentrations for subsequent cohorts.

Procedure	Study Days													Notes	
	1 and 7														
	-1	Predose	0	0.25	0.5	1	1.5	2	4	6	8	12	16		
12-lead safety electrocardiogram	X	X*				X		X	X	X	X	X		*Triplicate 12-lead safety ECGs will be obtained no more than 15 minutes apart within 1-hour pre-dose on Days 1 and 7.  Single 12-lead safety ECGs will be obtained at 1, 2, 4, 6, 8, 12 and 24 hours after study administration on Days 1 and 7.	
Continuous cardiac monitoring**		X*	Continuous review												**Participants will be semi-supine resting for at least 10 minutes prior to and 5 minutes after each time point for ECG extractions.  *3 time points (-45, -30 and -15 minutes) prior to dosing on Day 1.  When ECG extractions coincide with safety ECGs, vital signs assessment and blood draws, procedures should occur in that order.

Procedure	Study Days													Notes	
	1 and 7														
	-1	Predose	0	0.25	0.5	1	1.5	2	4	6	8	12	16		
Clinical chemistry (including liver chemistries), hematology, and urine tests (including urine creatinine)	X														
PK Blood Sample		X		X	X	X	X	X	X	X	X	X	X	Details of PK sample collection and storage will be provided in the Study Reference Manual.	
4β-hydroxycholesterol sampling		X												Sample to be taken pre-dose on Day 1 in a fasted state.	
Metabolite Blood Sample		X		X	X	X	X	X	X	X	X	X	X		
PK/Metabolite Urine Sample	X		See urine collection times*											*Urine collection times (hours) 0-2, 2-4, 4-6, 6-8, 8-10, 10-12, 12-22, 22-24 post dosing.  Participants will void bladder prior to dosing. 0-24-hr urine samples will be collected.  Voids from urine will be combined into 0-24 hr pool for metabolite analysis, after aliquots for PK are removed.	

Procedure	Study Days 1 and 7													Notes
	-1	Predose	0	0.25	0.5	1	1.5	2	4	6	8	12	16	
Genetic sample (optional)		X												Collect the genetic sample only if the participant has a signed consent specific for this purpose. Informed consent for optional sub-studies (e.g., genetics research) must be obtained before collecting a sample.
Stool microbiome collection/ stool type assessment*	X	*Continuous stool type assessment of all bowel movements while in the clinical unit.												Participants will be given instructions and collection items for specimen collection.  The stool sample can be collected up to 72 hours (3 days) prior to the visit the stool sample is required (Day -1).

Procedure	Study Days													Notes	
	1 and 7														
	-1	Predose	0	0.25	0.5	1	1.5	2	4	6	8	12	16		
Meal (post-dose)	X	See Notes for meal times													
Daily fluids (intake/output)		X*	See assessment times.												

AE = adverse event, BP = blood pressure, HR = heart rate, PK = Pharmacokinetic, SAE = serious adverse event.

24-hour procedures are presented in [Table 4](#).

The 4 $\beta$ -hydroxycholesterol sample may not be available from all Cohorts in Part 2, due to the timing of the amendment when this was added.

- The timing and number of planned study assessments, including: safety and pharmacokinetic assessments may be altered during the study based on newly available data (e.g., to obtain data closer to the time of peak plasma concentrations) to ensure appropriate monitoring.

- Any changes in the timing or addition of time points for any planned study assessments as the result of emerging pharmacokinetic/pharmacodynamic data from this study must be documented and approved by the relevant study team member and then archived in the sponsor and site study files but will not constitute a protocol amendment. The Competent Authority (CA) and ethics committee (EC) will be informed of any safety issues that constitute a substantial amendment and require alteration of the safety monitoring scheme or amendment of the informed consent form (ICF). The changes will be approved by the CA and the EC before implementation.

**Table 4 Part 2 – 7-Day Repeat Dose Escalation (Days 2 through 6 and Day 8 to 12)**

Procedure	Study Days								Notes
	2 (24hrs post-Day 1 dose)	3	4	5	6	8 (24 hrs post-Day 7 dose)	9-12		
Brief physical examination	X	X	X	X	X		X	X*	*Upon discharge
Administration of study intervention	X	X	X	X	X				No minimum time interval is required between the sentinels at each dose level. Approximately 15 minutes will be observed between the dosing of the remaining participants
AE Review	Continuous review								
SAE Review	Continuous review								
Ad hoc COVID-19 testing based on clinical presentation and site procedures	Continuous review							X*	*Sample collected just prior to discharge for COVID-19 testing
Concomitant medication review	Continuous review								

Procedure	Study Days								Notes
	2 (24hrs post-Day 1 dose)	3	4	5	6	8 (24 hrs post-Day 7 dose)	9-12		
Vital signs (BP, HR, tympanic temperature, respiration rate)	X		X	X	X	X		X	Single measurements will be obtained within 1-hour pre-dose and daily in the morning on days 9-12 until discharge.  Timings will be reviewed as cohorts progress and may be adjusted to ensure appropriate measurements relative to peak concentrations for subsequent cohorts.
12-lead safety electrocardiogram	X		X	X	X	X		X	Single 12-lead safety ECGs will be obtained within 1 hour before pre-dose and daily in the morning on days 9-12 until discharge.

Procedure	Study Days								Notes
	2 (24hrs post-Day 1 dose)	3	4	5	6	8 (24 hrs post-Day 7 dose)	9-12		
Continuous cardiac monitoring**	X					X			**Participants will be semi-supine resting for at least 10 minutes prior to and 5 minutes after each time point for ECG extractions.  When ECG extractions coincide with safety ECGs, vital signs assessment and blood draws, procedures should occur in that order.
Clinical chemistry (including liver and kidney chemistries), hematology, and urine tests (including urine creatinine)		X	X	X	X		X	X*	*Just prior to discharge.
PK Blood Sample	X		X*	X*	X*	X*	X		*Trough PK samples
4β-hydroxycholesterol sampling						X			Sample to be taken at 24hr post AM dose on Day 7. Sample should be in a fasted state.
PK Metabolite Sample	X						X		
PK Urine Sample	X		X*	X*	X*	X*	X		*Trough PK samples

Procedure	Study Days								Notes
	2 (24hrs post-Day 1 dose)	3	4	5	6	8 (24 hrs post-Day 7 dose)	9-12		
Stool microbiome collection/ stool type assessment*	*Continuous stool type assessment of all bowel movements while in the clinical unit.								X**  A last sample will be collected on the day closest to the day of discharge.  The stool sample can be collected up to 72 hours (3 days) prior to the visit the stool sample is required (Days 9-12).  **This includes the last sample collected on the day closest to the day of discharge (Days 9-12) for microbiome.  The Day -1 sample is indicated in SoA Table 4 and follow-up sample is indicated in SoA Table 1 .
Meal		X	X	X	X			X	Participants will receive standardized meals scheduled at the same time in each period.
Daily fluids (intake/output)	X					X			

Procedure	Study Days								Notes
	2 (24hrs post-Day 1 dose)	3	4	5	6	8 (24 hrs post-Day 7 dose)	9-12		
Discharge							X	X	Participants will be discharged from the clinical unit after the assessments are completed.

AE = adverse event, BP = blood pressure, HR = heart rate, PK = Pharmacokinetic, SAE = serious adverse event.

The 4 $\beta$ -hydroxycholesterol sample may not be available from all Cohorts in Part 2, due to the timing of the amendment when this was added.

- The start of Part 2 can be modified from emerging data from Part 1.
- The timing and number of planned study assessments, including: safety and pharmacokinetic assessments may be altered during the study based on newly available data (e.g., to obtain data closer to the time of peak plasma concentrations) to ensure appropriate monitoring.

Any changes in the timing or addition of time points for any planned study assessments as the result of emerging pharmacokinetic/pharmacodynamic data from this study must be documented and approved by the relevant study team member and then archived in the sponsor and site study files but will not constitute a protocol amendment. The Competent Authority (CA) and ethics committee (EC) will be informed of any safety issues that constitute a substantial amendment and require alteration of the safety monitoring scheme or amendment of the informed consent form (ICF). The changes will be approved by the CA and the EC before implementation.

## 2. INTRODUCTION

GSK3882347, a FimH (bacterial adhesin) antagonist, is a potent, novel non-antibiotic that is being developed for the treatment of uncomplicated urinary tract infections caused by uropathogenic Escherichia coli (UPEC).

### 2.1. Study Rationale

The goal of this study is to evaluate the safety, tolerability and pharmacokinetic properties (including food effect) of GSK3882347 to enable clinical development of the molecule as an antibiotic-sparing treatment for uncomplicated urinary tract infections.

Bacteria possess adhesins, which are cell-surface components or appendages that facilitate adhesion or adherence to other cells or to surfaces. GSK3882347 is a potent and specific competitive antagonist of the *Escherichia coli* type 1 pilus adhesin molecule FimH, designed to disrupt the interaction between FimH and mammalian mannose-rich glycoproteins, such as uroplakin Ia and integrins in the bladder epithelium and other epithelia.

GSK3882347 is being developed as an antibiotic-sparing medicine to treat or prevent infection of the bladder mucosa, via inhibition of FimH protein function on UPEC, which cause approximately 85% of all urinary tract infections. It is anticipated that the use of GSK3882347 will help combat the increasing antimicrobial resistance (AMR) to traditional antibiotics that threatens to increase greatly the economic burden, morbidity and mortality associated with bacterial infections [O'Neill, 2016].

Preclinical data in a murine urinary tract infection (UTI) model supports the use of a FimH antagonist in both the treatment and prevention of uncomplicated UTI (uUTI) in both infection naïve mice and previously infected mice (a recurrent UTI (rUTI) model). *In vitro* data indicate that GSK3882347 is an effective antagonist of FimH in a broad range of clinical UPEC strains. Further, GSK3882347 was effective against a subset of these strains representing all the major UPEC FimH alleles in both the murine UTI treatment model and in an *in situ* human bladder tissue binding assay. GSK3882347 inhibited binding in a concentration-dependent manner by >95% at 30  $\mu$ M (or less). *In vivo* efficacy studies were also completed using the acute therapeutic model in mice with UPEC strain UTI89 to correlate microbiological efficacy and urinary exposure. A preliminary PK/PD target for GSK3882347 was determined as the maintenance of a trough concentration of  $\geq$ 5  $\mu$ M in urine for the duration of the dosing period. Based on the studies described above, a target Cmin concentration range of 5-30  $\mu$ M was defined to support dose selection in this study.

### 2.2. Background

UTIs are very common, with approximately 11% of women >18 years of age experiencing at least 1 episode of acute cystitis per year [Foxman, 2000]. Of these, half will experience more than 1 recurrent episode over their lifetime [Foxman, 2000]. The peak incidence of acute cystitis occurs in young, sexually active women ages 18 to 29 years [Fihn, 2003]. The predominant uropathogen isolated in community-acquired

UTIs is *E. coli* (75% to 90%) followed by *S.saprophyticus* (5% to 15%) [Stamm, 1993; Talan, 2000; Foxman, 2010]. *Klebsiella*, *Enterobacter*, and *Proteus* species and enterococci are observed in only 5% to 10% of cases [Stamm, 1993; Talan, 2000; Foxman, 2010].

Multidrug resistance, which is typically associated with nosocomial infections, has now emerged at the community level and has made treatment approaches for UTIs more difficult [Hooton, 2012; Flamm, 2014; Sanchez, 2016]. This has led to increasing patient morbidity, increasing costs due to reassessment and retreatment, higher rates of hospitalization, and increased use of broad-spectrum antibiotics [Foxman, 2002; Gupta, 2011a; Hooton, 2012].

Due to the increase of more resistant strains, guidelines for acute cystitis now recommend first-line antibiotic treatment with nitrofurantoin, trimethoprim-sulfamethoxazole (TMP- SMX), fosfomycin, or pivmecillinam, assuming the drug is available and the patient does not have a concerning allergy history or tolerance issues [Gupta, 2011b]. TMP- SMX should not be used as a first-line treatment if the prevalence of resistance exceeds the 20% threshold or if TMP-SMX was used for treatment of a UTI in the previous 3 months. If any of these are concerns for a patient, then fluoroquinolones or  $\beta$ -lactams are recommended.

Continuous low dose antibiotic is effectively prophylaxis for recurrent urinary tract infections (rUTI). Other options include postcoital antibiotic prophylaxis prevention in sexually active females, vaginal estrogen in postmenopausal women, other treatments and behavioural modifications. With the rise of antibiotic resistance, additional treatment strategies and prevention measures for rUTI has led to potential non-antibiotic treatment approaches for rUTI.

GSK3882347 will be the first antibiotic-sparing medicine to treat or prevent infection of the bladder mucosa, via inhibition of FimH protein function on uropathogenic *E. coli* (UPEC), which cause approximately 85% of all UTIs. Use of GSK3882347 will help combat the increasing antimicrobial resistance (AMR) to traditional antibiotics that threatens to increase greatly the economic burden, morbidity and mortality associated with bacterial infections [O'Neill, 2016].

Summaries of the non-clinical safety and pharmacology are included in the GSK3882347-Investigator's Brochure [GlaxoSmithKline Document Number 2019N403317\_01, 2020].

In light of the global COVID-19 pandemic, all participants will be screened for COVID-19 prior to, during and at the end of the study period. Please see further details for risk assessment and mitigation strategy below.

## 2.3. Benefit/Risk Assessment

### 2.3.1. Acute Monitoring in FTIH Studies

Consistent with GSK standards for early phase studies, the study will be conducted in a Phase 1 Clinical Research Unit with previous experience with first-time-in-human trials and immediate access to hospital facilities for the treatment of medical emergencies.

GSK3882347 will be administered in an in-patient setting (with sufficient overnight facilities) with appropriate monitoring. To minimize the risk of the initial human administration of GSK3882347, a sentinel dosing strategy will be utilized at each dose level: 1 participant will receive GSK3882347 and 1 participant will receive placebo. After the GSK Medical Monitor and Principal Investigator have reviewed the safety data through 24 hours post-dose in the Part 1 and at least 120 hours in Part 2, the remaining participants from that cohort will be dosed.

Once all assessments through 24 hours post-dose have been completed in a minimum of four participants on active treatment in Part 1 and at least 7 days of dosing in a minimum of 5 participants on active treatment in Part 2, the GSK team and the investigator will review all the available safety and PK data from all participants before proceeding to the next dose level. Additional information can be found in the Dose Escalation Plan. More detailed information about the known and expected benefits and risks and reasonably expected adverse events of GSK3882347 may be found in the GSK3882347 Investigator's Brochure [GlaxoSmithKline Document Number [2019N403317\\_01](#), 2020]. The following section outlines the risk assessment and mitigation strategy for this protocol:

### 2.3.2. Risk Assessment

Potential Risk of Clinical Significance	Summary of Data/Rationale for Risk	Mitigation Strategy
Investigational Product (IP) GSK 3882347		
Gastrointestinal toxicity (including body weight loss, decreased food consumption and dehydration)	
Dogs given <math>\geq 300</math> mg/kg/day had severe body weight loss, decreased food consumption, dehydration, emesis and abnormal feces. Dogs given 1000 mg/kg/day were euthanized early due to severity of body weight loss.
 
Pregnant rabbits given <math>\geq 300</math> mg/kg/day had severe body weight loss and decreased food consumption, which resulted in early euthanasia and 1 early death at 900 mg/kg/day.
 
These changes in dogs and rabbits resulted in early euthanasia or death at the doses stated. Nonclinical Risks – concluding sections of the Non-Clinical Assessment of Safety (NCAS) should provide key nonclinical risks associated with the IP.
	
 
• Dosing for a maximum of 7 days.
 
• Standard clinical monitoring with elicitation of clinical symptoms; physical examinations and routine safety blood haematology and chemistry tests.
 
• Monitoring for AEs.
 
• Monitoring daily fluid balance in participants.
 
• Gastrointestinal stopping criteria: Participant will continue to dose through grade 1 toxicity, interrupt dosing for grade 2 toxicity and discontinue drug for grade 3-4 toxicity (for the latter, consultation with GI experts will occur with no plan for drug restart) (see Section 7.1.1)
 
• Monitoring of stool type with the Bristol stool chart to identify changes in bowel
 

Potential Risk of Clinical Significance	Summary of Data/Rationale for Risk	Mitigation Strategy
		habit which may represent gastrointestinal toxicity.
OTHER		
COVID-19	
Participation within a hospital environment may increase risk of contracting COVID-19.
 
Exposure to other participants and staff may increase risk of exposure.
	

• Monitoring of clinical presentation of COVID-19 signs/symptoms.

• Conduct study at sites which have appropriate mitigation strategies in place.

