#### 7.1.1. Gastrointestinal Events (diarrhea or colitis)

[figure not shown]
Grade	Diarrhea	Management	Follow-up
Mild (Grade 1)  An event that is easily tolerated by the participant, causing minimal discomfort and not interfering with everyday activities	Increase of <4 stools per day over Baseline	
 
Administer antidiarrheal and symptomatic treatment as appropriate
 
Discuss participant continuation in the trial with Sponsor/Medical Monitor
 
	
Symptoms resolve to baseline within 3 days:
 
 
Provide close follow-up to evaluate for increased severity.
 
 
Symptoms ongoing > 3 days:
 
 
Consider following algorithm for Grade 2 events
 

Moderate (Grade 2)  An event that causes sufficient discomfort and interferes with normal everyday activities	Increase of 4 - 6 stools per day over Baseline	
 
Interrupt study drug(s)
 
Administer antidiarrheal and symptomatic treatment
 
Investigate etiology; consider consulting GI service
 
Discuss participant continuation in the trial with Sponsor/Medical Monitor
 
	
Symptoms resolve to ≤ Grade 1 or baseline within 7 days:
 
 
Continue follow-up and evaluate for any increased severity.
 
 
Symptoms ongoing > 7 days, blood or mucus in stool, or ulceration/bleeding on endoscopy:

Grade	Diarrhea	Management	Follow-up
			
 
Consider following algorithm for Grade 3 events
 

Severe (Grade 3-4) An event that prevents normal everyday activities	Grade 3: Increase of $\geq 7$ stools per day over Baseline; incontinence; hospitalisation indicated  Grade 4: life-threatening consequences; urgent intervention indicated	
 
Discontinue study drug(s)
 
Consult GI service
 
Discuss participant continuation in the trial with Sponsor/Medical Monitor
 
	
Symptoms ongoing:
 
 
Continue follow up of participant
 
Discuss further management with GI consultant and Sponsor/Medical Monitor
 

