### 7.1.4. Individual Stopping Criteria

- Any participant who experiences an SAE will be withdrawn from the study.
- Any participant who experiences an AE of moderate or severe intensity that is considered attributable to dosing with GSK3882347 will be withdrawn from the study.
- If a participant develops COVID-19 like symptoms during the course of the study the following actions should be taken:
  - During Part 1 (SAD portion of the study), participants who develop a high clinical index of suspicion for COVID-19 disease should be isolated and tested for COVID-19 in accordance with site procedures.
  - During Part 2 (MAD portion of the study), study treatment should be halted for any participants who develop a high clinical index of suspicion for COVID-19 disease; they should be isolated and tested for COVID-19 in accordance with site procedures.
  - In both cases, assessments should be continued as per the protocol during this period; withdrawal of participants from the study will be at the discretion of the Principal Investigator, but should first be discussed and agreed with the GSK Medical Monitor.

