## 7.2. Study Stopping Criteria

In the event of any of the following, ongoing dosing will be halted and no new participants will be dosed at this dose level. A safety review will be undertaken; following this review an additional cohort may be enrolled at a lower dose level.

- An SAE that is related to GSK3882347 in one or more participants on active treatment.
- Two similar AEs of moderate intensity in 2 or more participants.
- Two AEs of severe intensity (but not necessarily similar) in 2 or more participants.
- Finally, if a sentinel participant receiving GSK3882347 meets any of these clinical stopping criteria, the rest of the Period (SAD) or Cohort (MAD) will not be dose and further dose escalation will not occur (see Section 7).

Dosing at the current (higher or lower) dose may resume only following approval of a substantial amendment by the MHRA as well as the ethics committee.

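### The gastrointestinal stopping criteria that section 2.3.2 relies on visibly cover only diarrhea or colitis, and body weight is scheduled only at screening, so scheduled data cannot show on-treatment weight loss

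*Protocol*

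**What the plan says.** Protocol section 2.3.2 has one entry under the investigational product: gastrointestinal toxicity, "including body weight loss, decreased food consumption and dehydration". The supporting animal data add emesis in dogs. They report early euthanasia of dogs at 1000 mg/kg/day because of the severity of weight loss. Among the mitigations, beside adverse-event monitoring, fluid balance, laboratory tests, examinations and stool typing, is this rule: "Participant will continue to dose through grade 1 toxicity, interrupt dosing for grade 2 toxicity and discontinue drug for grade 3-4 toxicity". The rule states no causality condition and points to section 7.1.1.

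Section 7.1.1 is headed "Gastrointestinal Events (diarrhea or colitis", and its criterion column is labelled for diarrhea. Grade 2, for example, is "Increase of 4 - 6 stools per day over Baseline". The Grade column beside it carries general intensity wording, for moderate "An event that causes sufficient discomfort and interferes with normal everyday activities". The Grade 2 action is to interrupt study drug and discuss continuation. The Grade 3-4 action is to discontinue.

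Section 7.1.4 says: "Any participant who experiences an SAE will be withdrawn from the study". It also says that any participant with an "AE of moderate or severe intensity that is considered attributable to dosing with GSK3882347 will be withdrawn from the study". Section 7.2 halts dosing for a related serious event, for "Two similar AEs of moderate intensity in 2 or more participants", or for severe events, similar or not, in two or more participants.

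For weight, Table 1 of the Schedule of Activities places the full examination, with height and weight, at screening only. Section 8.2.1 gives a minimum content for the brief examination that does not include weight.

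**The concern.** Section 2.3.2 makes a promise about a broad risk and hands it to a section whose visible criteria cover one manifestation of that risk. A site applying section 7 to a participant who is vomiting, dehydrated or not eating finds no criterion in 7.1.1 that speaks to those signs. Weight loss, the sign for which dogs were euthanized, has no scheduled measurement after screening, so no rule could act on it from planned data.

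At stake is whether the protocol does what its risk table says for the one drug-specific risk it lists, in a first-in-human study of participants who gain no medical benefit. There is also a tension inside section 7. For a moderate diarrheal event attributed to the drug, 7.1.1 says to interrupt and discuss, while 7.1.4 says the participant is withdrawn.

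**Working it through.** No sample size or error rate is involved. The check compares rules and counts scheduled weights.

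**1. Which section 7 rules reach a non-diarrheal gastrointestinal event?** Take vomiting, dehydration or decreased intake of moderate or severe intensity.

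- 7.1.1: no visible criterion is met. Grades 1 and 2 rest on stool counts, Grade 3 adds incontinence or an indication for hospitalisation, and Grade 4 is life-threatening consequences, all in the diarrhea column. The intensity wording in the Grade column could describe such an event, but nothing says the actions extend to it.
- 7.1.4, serious event: withdrawn, whatever the cause.
- 7.1.4, moderate or severe and attributable: withdrawn.
- 7.2: dosing halts for a related serious event, for similar moderate events in two or more participants, or for severe events in two or more. The sentinel clause reuses these criteria.
- 7.3 and section 8: withdrawal at the investigator's discretion, and discussion with the sponsor. Both permit a stop; neither mandates one.

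The case left over is one participant with a non-serious event judged unrelated. Such a case can exist. Section 10.3.3 separates severe from serious. Section 10.3.2 says uncomplicated vomiting does not meet the disability criterion even when it prevents everyday functions, so it would need another criterion, such as hospitalisation, to be serious.

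**2. Does 2.3.2 require a stop in that case?** It depends on the word toxicity.

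- Read without attribution, 2.3.2 requires interruption or discontinuation and section 7 does not clearly do so. The gap is real but confined to the case above.
- Read as a drug effect, an event judged unrelated is not toxicity, and 7.1.4 covers the attributable ones. The gap closes, but 2.3.2 and 7.1.1 then say interrupt at Grade 2 where 7.1.4 says withdraw.

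Either reading leaves a sentence to write.

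**3. Can scheduled data show weight loss in Part 2?**

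- Scheduled weights: 1, at screening, up to 30 days before Day 1 (Table 1).
- Day 1 to the Day 7 dose is 6 days, so the value can be 30 + 6 = 36 days old at the last dose.
- Later scheduled examinations, all brief: 1 on Day -1 (Table 3) + 7 marks in Table 4 + 1 at follow-up (Table 1) = 9.
- Of these 9, the number that list weight is 0.

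With one scheduled value per participant, no change from baseline can be computed. An unscheduled weight taken during the stay would be compared with a value up to 36 days old, so the difference would mix change before dosing with change on treatment.

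**The case against.** The strongest reply is that toxicity in 2.3.2 means a drug effect. The rule sits in the investigational-product block, and the same cell speaks of bowel changes that may represent toxicity, which separates a symptom from its cause. On that reading 7.1.4 already goes further than 2.3.2 at Grade 2. This is a fair reading and it stands: 2.3.2 states no causality condition, but that does not show it was meant to cover unrelated events.

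The residual case is also small and supervised. Participants are in-house with continuous adverse-event review. The investigator must weigh timing and the Investigator's Brochure when judging causality, and doubtful hospitalisation counts as serious. Leaving a single unrelated event to judgement is defensible. One figure in 7.1.1 is not available to this review, so the point is limited to the visible text, although the section heading itself restricts the scope.

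On weight, 2.3.2 does not list weighing as a mitigation, so nothing is contradicted. The brief examination is a minimum list, and Table 1 allows a brief examination to be made full where findings indicate. These points show that a weight can be obtained, not that one will be. They do not answer the absence of a scheduled on-treatment value or of a baseline close to dosing.

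The animal findings also need proportion. The highest planned dose is 900 mg, and the predicted steady-state exposure on dog pharmacokinetics, 107 µg*h/mL, is below the rat no-adverse-effect exposure of 193 µg*h/mL (193/107 = 1.80-fold). That lowers the expected frequency of such signs; it does not replace measuring them.

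**Conclusion.** The point holds as a minor safety improvement. Two things rest on the text alone: the visible 7.1.1 criteria do not operationally reach the non-diarrheal signs that 2.3.2 names, and no scheduled data can show weight loss on treatment. A third is a plain conflict: interruption under 7.1.1 against withdrawal under 7.1.4 for an attributable moderate diarrheal event.

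A reader might infer that non-diarrheal gastrointestinal toxicity has no stopping rule, or that participants would be dosed through it. The documents do not support that. Serious events, attributable moderate or severe events, and events in two or more participants are covered by 7.1.4 and 7.2. The remaining stopping gap is a single non-serious event judged unrelated, and it exists only if toxicity is read without attribution.

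The protocol gives no basis for estimating how often that case would arise. The number of participants or of doses still to be given would be an upper bound on reach, not a measure of risk, so no such figure is offered.

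**What to change.** 1. In the Schedule of Activities, add body weight on Day -1 and on set days of the Part 2 in-house stay through discharge. Assess weight loss as percent change from Day -1, with a threshold chosen by the sponsor, since the protocol gives none. The everyday-activities wording is not a workable scale for weight.
2. In 7.1.1, state that the Grade 2 and Grade 3-4 actions also apply to vomiting, dehydration and decreased intake, graded by the intensity wording already in the Grade column, and widen the heading to match. Say whether this holds regardless of attribution, which settles the meaning of 2.3.2.
3. In 7.1.1, state that withdrawal under 7.1.4 takes precedence when the event is attributable to the drug.

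The cost is a few sentences and a few scale readings during stays that are already in-house. If the actions apply regardless of attribution, there will be an occasional interruption for a truly unrelated event, with some loss of repeat-dose pharmacokinetic data in that participant.
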